10.5.1.2.6 Maximum Injection Volume per IOH

Total maximum volume for initial injection or delayed-treatment injection is 1.0 mL per IOH; total maximum volume for touch-up injection is 0.5 mL per IOH. Subjects may receive no more than 1.0 mL per IOH at retreatment.

Total volume administered per IOH for the study should not exceed 2.5 mL for the treatment groups (TN and TC) or 1.5 mL for the control/delayed-treatment groups (CDTN and CDTC).

10.6 Previous and Concomitant Non-drug Therapies

Previous therapies received prior to enrollment and concomitant therapies should be documented in the eCRF.

Restrictions regarding prior or concomitant non-drug therapies are discussed in detail in Sections 9.2.2 (Exclusion Criteria) and 9.2.3 (Restrictions during the Study).

10.7 Study Supplies and Packaging of Treatment Supplies

BBL and study accessories (needle, cannula pack) will be provided by the sponsor. The sponsor will package study materials according to applicable regulatory requirements. The sponsor will provide all pertinent labeling information as well as a description of the specific device-packaging conditions.

BBL is to be used exclusively for treatment of subjects enrolled in this study and will be labeled as follows: "CAUTION - Investigational Device. Limited by Federal (or United States) Law to Investigational Use." Device labels will also note the manufacturer name and address, as well as the quantity within the package. The IFU for the investigational product will be provided The clinical trial supply should be stored in a controlled area with limited access and stored separately from any commercial supplies.

The following components are supplied for the injection procedure:

- BBL box containing one sterile 1-mL prefilled glass syringe of BBL with two 27G ½" or 30G ½" needles.
 - o More than one BBL box may be used depending on injection volume.
 - O Use only the 27G ½" needles provided.
 - o If subject is randomized to cannula, these needles should not be used.
- A peel-off subject label, indicating product, to be placed in the source documents.
- A separate bulk supply of 27G 40 millimeter (mm) blunt-tipped cannula, with a 25G introductory needle, will be provided for the cannula-injection procedure.

In the event of a pandemic disease outbreak (e.g., new COVID-19 public health emergency), considerations may be made to supply study sites with sufficient study supplies to avoid interruptions to the supply chain for the investigational product during the outbreak.

10.8 Receipt, Storage, Dispensing, and Return/Disposal

Upon receipt, site personnel will verify the contents of all study supplies received and promptly notify the appropriate contacts of any discrepancies or damages. The investigator is responsible for ensuring an accurate record of inventory is maintained. The investigator will keep a current record of the study-product delivery to the study site, inventory, and dispensing, and this record will be made available to the sponsor upon request. Study sites will be queried about any discrepancies.

All study devices must be stored in a secure, environmentally controlled, monitored area, in accordance with the labeled storage conditions.

Only authorized study personnel may supply, dispense, and/or administer study treatment, and only subjects enrolled in the study may receive study treatment. The investigator is responsible for maintaining a current, accurate record of all study-treatment dispensation.

Any used syringes of investigational device and needles or cannulas should be discarded per the appropriate handling and disposal procedures at the site. Any unopened product, needles, cannulas, and/or outer packaging of used kits should be retained so the monitor can perform device-accountability procedures.

At the end of the study and after verification of study device accountability, it is the investigator's responsibility to return all unused study supplies, as directed by the sponsor. Appropriate records of return must be maintained for accountability purposes.

All study-accountability procedures must be completed before the study is considered complete.

10.9 Device Accountability Procedures

The sponsor will provide the investigator with all necessary study supplies. Accountability for study supplies at the study site is the responsibility of the investigator.

Access to the IMD will be controlled, and IMD will be used only in the clinical investigation and according to the clinical study protocol. The sponsor will keep records to document the physical location of all IMDs from shipment to the investigation sites until return or disposal. The principal investigator or an authorized designee will keep records documenting the receipt, use, return, and disposal of the IMDs, which will include the following:

- The date of receipt and quantity of units received.
- Identification of each IMD (batch number/serial number or unique code).
- The expiration date (if applicable).
- The names of all persons who received, used, or disposed of each device.
- The date(s) of use.
- Unique subject identification number.
- Date and quantity of units returned.
- The date of return of unused, expired, or malfunctioning IMDs (if applicable).

In the event of a pandemic disease outbreak (e.g., new COVID-19 public health emergency), considerations may be made to perform study-accountability procedures remotely and return of unused supplies may be delayed until return procedures can be safely performed by site personnel.

10.10 Treatment Compliance

Treatment is administered by the treating investigator and thus assessment of compliance is unnecessary. Potential deviations from the defined study-treatment administration will be reported as protocol deviations.

10.11 Duration of Study

The planned duration of participation for individual subjects from baseline to the end of the study is 76 weeks (\pm 14 days). In addition, subjects will also undergo a screening period up to 10 days and at least 3 days prior to the baseline visit.

In the event of a public health emergency the study might be halted, recruitment interrupted, and/or study processes and flow might be modified, impacting to the study duration and/or visit schedule depending on the study status at the time of the event. Mitigations may include, but are not limited to, extending visit windows, performing visits by phone or video, and/or performing effectiveness assessments remotely.

11 STUDY PROCEDURES

11.1 Visit Schedule

CCI

To determine subject eligibility for study participation, a screening evaluation must be completed from -10 to -3 days before baseline. Eligible subjects will be randomized at the screening visit.

After screening evaluation, each subject randomized to treatment will have between 10 and 14 visits, depending on whether he/she receives a touch-up and/or retreatment injection.

Subjects randomized to control will remain untreated until Week 8, when the primary effectiveness endpoint is evaluated. Upon completion of all effectiveness assessments, control subjects will be treated with BBL (i.e., will receive delayed treatment). After screening evaluation, each subject in the control/delayed-treatment group will have between 8 and 10 visits, depending on whether he/she receives a touch-up injection.

The primary endpoint visit will occur at Week 8 (+7 days) post last injection (i.e., initial injection or touch-up, if applicable) for the treatment group and at Week 8 (+7 days) after screening for the control/delayed-treatment group.

For subjects in the treatment group, the final visit will occur 72 weeks (± 14 days) post last injection (initial or touch-up, if applicable) or 24 weeks post retreatment (if applicable).

For subjects in the control/delayed-treatment, the final visit will occur 48 weeks (\pm 14 days) post last injection (initial or touch-up, if applicable).

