9 STUDY POPULATION AND RESTRICTIONS

9.1 Number of Subjects and Sites

A total of 150 subjects will be randomized at up to 9 investigational sites in the US. At each study site, the number of subjects randomized should not exceed 26. A minimum of 20% of the enrolled subjects will be Fitzpatrick Skin Type IV, V, or VI. Subjects from the Fitzpatrick Skin Type IV, V, or VI group will be distributed as follows: at least 16 subjects of Type IV, 7 subjects of Type V; and 7 subjects of Type VI. At least 10% of the subjects enrolled will be male.

Any randomized subject who does not complete the study will not be replaced.

Additional information regarding subject enrollment is provided within the sample size justification in Section 13.2.

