11.2.2.2 Other Safety Assessments

11.2.2.2.1 Visual-Function Assessments

Although the incidence of AEs/SAEs associated with retinal artery occlusion is very low, treated subjects will undergo visual examinations to potentially identify ophthalmic signs and/or symptoms that may represent ophthalmic-artery occlusion.

Visual-function assessments will include a visual-acuity test (using a Snellen chart), a confrontation-visual field test, and an ocular-motility examination. These assessments will be completed at screening, pre-treatment, post-initial injection, pre- and post-treatment for

the touch-up and retreatment injections (if applicable), pre- and post-treatment for the delayed-treatment injections, and at all follow-up visits

The aforementioned visual safety assessments can be performed by the treating investigator or a trained delegate. The subject's vision will be assessed wearing the same permitted spectacle correction and in the same exam room to help to control for differences in room lighting and other conditions.

In addition, undilated retinal photographs will be taken at the screening visit (pre-treatment), after initial treatment, after touch-up injection, if applicable, and at the optional retreatment visit before and after injection Photographs will be captured using non-mydriatic retinal cameras and will be read by a central ophthalmic imaging center (central reader).

Any abnormality identified during the visual-function assessments at screening and/or before initial injection should be documented as medical history. Following the screening visit, if the central reader detects a clinically relevant visual pathology that may potentially interfere with study results or potentially enhance the safety concerns of a subject as a result of treatment, the subject will need to be evaluated for whether he/she meets one or more exclusion criteria and should not be treated.

Visual-function assessments will be performed 30 minutes after treatment of each IOH. The contralateral IOH should not be treated until the visual-function assessments are performed on the treated side, and no clinically significant changes are noted. Additionally, retinal photographs of both eyes will be taken 30 minutes after completion of treatment of both IOHs.

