The examiner should determine if the subject's range of ocular movement is intact in each direction of gaze. The examination should be performed without the subject wearing glasses (note: contacts are permitted). To begin, the subject should be asked to look at a distant object while his/her head is facing straight ahead. The subject's head should not be tilted up, down or to the side. Symmetry between the eyes should be noted in primary position. The subject should then be asked to follow the examiner's finger without the subject moving his/her head. The examiner should use his/her index finger on either the right or left hand for guiding the direction of eye movement. The investigator should move the index finger to the left, right, up and right, up and left, down and left, down and right, straight up and straight down. The subject should be asked to voice if he/she experiences double vision in any position of gaze and/or in any of the fields. The examiner should look for and document any asymmetry in ocular motility or abnormal ocular motility.

11.2.2.2.1.4 Undilated Central Retinal Exam Using a Non-mydriatic Retinal Camera

In this procedure, the treating investigator or delegate will take pictures of the undilated central retina and blood vessels using a non-mydriatic retinal camera system. Note: pictures must be taken without the subject wearing glasses or contacts. Subsequently, images will be uploaded and remotely evaluated by a specialist at a central ophthalmic imaging center. The investigational site will receive an assessment report from the central ophthalmic imaging center within 24 hours. If any retinal findings are noted, the site will contact the subject and the site-identified ophthalmology practice to arrange an immediate evaluation.

11.2.2.2.1.5 Directions for Intravascular Injection or Embolic Event

Each site will identify a local ophthalmology practice that is equipped and qualified to address any visual changes and a potential retinal artery occlusion that may occur as a result of injection (i.e., clinically significant changes in vision, such as blindness, blurriness, double vision, pain in or around the eye [other than typical injection-induced pain], blind spots, or restriction of eye motility).

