13.1 Randomization

Subjects who complete all screening assessments and meet all eligibility criteria will be randomized to the following four groups:

- Group TN: Treatment with BBL with needle at baseline;
- Group TC: Treatment with BBL with cannula at baseline;

- Group CDTN: Untreated control until Week 8 / Delayed-treatment BBL with needle (starting at Week 8);
- Group CDTC: Untreated control until Week 8 / Delayed-treatment BBL with cannula (starting at Week 8).

Randomization will be block-stratified by investigational site, and groups will be assigned via an electronic system linked to the eCRF. At each study site, the number of subjects randomized should not exceed 26 to ensure a reasonable distribution of subjects across all investigational sites.

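### Subjects are randomized at the screening visit, before a central retinal read that can still exclude them, and the ITT definition then treats such subjects differently by arm

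*Protocol*

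**What the plan says.** **When subjects are randomized.** Protocol 11.1 states: "Eligible subjects will be randomized at the screening visit". Section 8.3.1.1 repeats this, and Protocol 8.1 and SAP 2.1 also put allocation at screening. Section 11.1 adds that "a screening evaluation must be completed from -10 to -3 days before baseline".

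**When the retinal read arrives.** Retinal photographs are taken at the screening visit and uploaded for remote reading. Under 11.2.2.2.1.4, "The investigational site will receive an assessment report from the central ophthalmic imaging center within 24 hours".

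**What the read can do.** Section 11.2.2.2.1 begins the rule with "Following the screening visit, if the central reader detects a clinically relevant visual pathology that may potentially interfere with study results", or may raise the safety concern for that subject. In that case "the subject will need to be evaluated for whether he/she meets one or more exclusion criteria and should not be treated".

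**The other rule on sequence.** Protocol 13.1 says: "Subjects who complete all screening assessments and meet all eligibility criteria will be randomized to the following four groups". Section 10.3 says the same of assigning a randomization number.

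**What happens to the subject.** Section 9.1 states: "Any randomized subject who does not complete the study will not be replaced". Section 9.2.4 defines screen failures by ineligibility or by withdrawal of consent, with a clause about being before randomization that can be read as covering both or only the second. The primary analysis set (ITT(1) in Protocol 13.3, ITT in SAP section 4) takes every randomized control subject but only those TRT subjects who were both randomized and treated.

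**The concern.** Eligibility should be final before the arm is assigned. Here one check that can stop a subject from being treated comes afterwards, and it is triggered by a judgment that a finding might interfere with results or safety. Nothing in the visible text withholds the assignment until the report is back. Only the MIHAS evaluators and the photograph panel are described as blinded. The treating investigator performs the injections (10.5) and must know the arm by Day 1.

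The analysis set turns this timing into a difference between arms. The same retinal finding removes a TRT subject from the primary comparison and leaves a CTL subject in it. At stake is whether the two groups compared at Week 8 are the two groups that were randomized.

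**Working it through.** **1. Order of events**

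| Step | Time | Source |
|---|---|---|
| Retinal photographs | Screening visit | Protocol 11.2.2.2.1 |
| Randomization | Screening visit | Protocol 8.1, 8.3.1.1, 11.1; SAP 2.1 |
| Central report to site | Within 24 hours | Protocol 11.2.2.2.1.4 |
| Possible exclusion review | After the screening visit | Protocol 11.2.2.2.1 |
| Injection, TRT | 3 to 10 days after screening | Protocol 11.1 |
| Primary rating, then injection, control | 8 weeks after screening | Protocol 11.1 |

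Unless every report is returned before the visit ends, 8.3.1.1/11.1 and 10.3/13.1 cannot both be followed if the read counts as a screening assessment. Section 11.2.2.2.1 uses it as one.

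**2. The same finding in each arm**

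- TRT: the subject is stopped before injection, is not treated, and so is not in ITT. SAP 6.1.1.1 imputes missing Week 8 scores only for ITT subjects, so this subject is not imputed either.
- CTL: the subject is randomized and so is in ITT. No injection is due before the Week 8 rating, which can still be given; if it is missing, it is imputed.

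**3. The plan's own power figures, as a baseline**

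Inputs from Protocol 13.2: one-sided alpha 0.025; TRT 70%, CTL 30%, Step 1 null 50%; 80 and 40 analyzed; 20% drop-out.

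- Step 1, exact binomial, n = 80: reject at 50 or more responders; power 0.9413 (plan: at least 94%).
- Step 2, one-sided Fisher, 80 vs 40, full enumeration: power 0.9837 (plan: at least 98%).
- Overall: 0.9413 × 0.9837 = 0.926 (plan: above 92%).
- Total: 120 / (1 − 0.20) = 150 (plan: 150).

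All four reproduce, and this point changes none of them.

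**4. How many subjects could be affected**

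The documents give no rate, so r is an assumption. Expected counts are 100r in TRT and 50r in CTL; the chance of at least one in TRT is 1 − (1 − r)^100.

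| r | TRT | CTL | All 150 | At least one in TRT |
|---|---|---|---|---|
| 1% | 1 | 0.5 | 1.5 | 63% |
| 3% | 3 | 1.5 | 4.5 | 95% |
| 5% | 5 | 2.5 | 7.5 | 99% |

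**5. Power if k TRT subjects leave ITT**

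Drop-out is 20% among the rest, with 40 CTL subjects analyzed.

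| k | TRT analyzed | Step 1 | Step 2 | Product |
|---|---|---|---|---|
| 0 | 80 | 0.9413 | 0.9837 | 0.926 |
| 1 | 79 | 0.9501 | 0.9833 | 0.934 |
| 2 | 78 | 0.9319 | 0.9822 | 0.915 |
| 3 | 78 | 0.9319 | 0.9822 | 0.915 |
| 5 | 76 | 0.9211 | 0.9808 | 0.903 |

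The values are not monotone because the exact test is discrete.

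**6. How far the handling rule can move the result**

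Suppose instead that the k subjects stay in as non-responders, which is a harsh choice. The expected TRT rate is 0.70 × (100 − k)/100: 69.3% at k = 1, 68.6% at k = 2 and 66.5% at k = 5. Step 1 power at n = 80 is then 0.923, 0.901 and 0.810. At r = 5% in both arms, with the same rule in both, the CTL rate is 0.30 × 0.95 = 28.5%, and the expected difference is 66.5 − 28.5 = 38.0 points instead of 40.

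**The case against.** The strongest reply has five parts.

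- **Protocol 10.3 and 13.1 already require screening to be complete.** A site that follows them would wait for the report. This does not remove the problem, because 8.3.1.1 and 11.1 tell the same site to randomize at the visit.
- **The stronger readings are not in the text.** A reader might infer that an unblinded investigator decides eligibility with the arm in hand, or that allocation concealment has failed. Section 11.2.2.2.1 is in the passive and names no decision-maker. Detection is by an off-site central reader whose knowledge of the arm is not described. Assignment is by an electronic system, and no foreknowledge of it is shown. A reader might also infer that such subjects can never be screen failures, but the clause in 9.2.4 is ambiguous. All of this stands.
- **Much is not visible.** Most exclusion criteria, the schedule of events and the visual-assessment schedule are not shown. We cannot tell which criterion the read feeds or how objective it is. This stands, and it limits how much weight the subjective trigger can carry.
- **Bias needs more than timing.** The rule in 11.2.2.2.1 is the same for both arms. Removing a few TRT subjects distorts the comparison only if the finding, or the decision taken on it, is related to the rated MIHAS response. The documents offer no such link. This stands; the difference between arms comes from the ITT definition acting on a late exclusion.
- **It may be too late.** The Version 5.0 log says that all control subjects had already completed the visit 8 weeks after screening when the footnote error was noticed, which implies that accrual had ended. This stands for the timing change, but not for reporting and analysis.

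**Conclusion.** The point holds as a conflict of sequence with a consequence for the analysis set. Stated rules put one eligibility check after allocation, and the ITT definition makes the resulting exclusion differ by arm. That the arm is known when the decision is made is plausible, because no blinding of the treating investigator is described, but it remains an inference.

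The size is probably small. If 1 to 5 of 100 TRT subjects left ITT, overall power would stay at about 0.90 to 0.93, within the plan's 20% drop-out allowance. The Step 1 figure of 0.810 arises only if 5% of TRT subjects are affected and all are counted as non-responders. Every such figure rests on an assumed rate of findings. The change is worth making because it is cheap and removes a post-allocation exclusion, and because the plan has no explicit rule for classifying a subject found ineligible after randomization.

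**What to change.** **Timing.** Reword Protocol 8.1, 8.3.1.1 and 11.1 and SAP 2.1 so that subjects in all arms are randomized in the electronic system only after the central retinal report has been received and all eligibility criteria are confirmed. This should happen within the existing screening window, before the baseline injection visit for TRT. The control Week 8 clock still runs from the screening visit. Sections 8.3.1.1 and 11.1 then agree with 10.3 and 13.1.

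**Classification.** Reword 9.2.4 so that a subject excluded on the report before randomization is a screen failure.

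**Cost.** Protocol and SAP wording, about one day's delay, and a phone call to give the assignment and book the next visit. The 24-hour report fits the minimum 3-day gap, which the pandemic provision in 11.3 also keeps.

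**If accrual is already complete.** The timing change no longer helps this trial. Instead, report by arm the number of randomized subjects excluded on the screening retinal read. Add a sensitivity analysis of the primary endpoint that treats them the same way in TRT and CTL, for example all kept as non-responders or all removed. SAP 6 already tabulates reasons for discontinuation up to Week 8 by group, so the extra work is small.

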11.2 Study Assessments and Definitions

11.2.1 Effectiveness Assessments

Refer to the respective endpoints (see Section 7.2.1) for additional information including the timing of effectiveness assessments.

11.2.1.1 Merz Infraorbital Hollow Assessment Scale (MIHAS)

The MIHAS was designed to assess the infraorbital hollow that results from volume loss. Each grade of the MIHAS is distinct; Grade 0 is anchored to depict none to minimal signs of hollowing, and Grade 4 is anchored to depict extreme signs of hollowing

In the current study, the MIHAS will be used to detect clinically relevant, aesthetic changes as a result of volume correction in the IOH area.

For each of the five severity grades presented on the scale, three reference subjects are displayed. For each subject, a frontal view is presented to indicate specific characteristics of the IOH region. The left and right IOH of each subject is assessed independently on the MIHAS within this study.

During the baseline and subsequent study visits, subjects will be evaluated live on the MIHAS by a trained evaluator (i.e., a qualified healthcare practitioner delegated by the treating investigator); this evaluator is blinded to the subject's treatment assignment and will perform the respective assessment independently from any study staff. Prior to study enrollment, at least one blinded evaluator at each site will be trained and qualified by the study sponsor to perform scale-grading assessments. Training will consist of an instructional session, followed by a qualification where blinded-evaluator trainees will score two sets of photographs, representing a variety of different MIHAS grades, at least two weeks apart. The purpose of this assessment is to obtain intra- and inter-evaluator reliability qualification analyses prior to starting the study at their respective site (i.e., weighted Kappa/ICC analyses). Any blinded evaluator who does not successfully achieve an intra- and inter-rater (pair-wise against other raters) reliability point estimate value of ≥ 0.70 will be retrained and requalified up to two times. If evaluator retention (e.g., change in personnel) becomes an issue during the study, new blinded evaluators must be trained by the sponsor, and respective qualification analyses must be performed. Qualification and training of blinded evaluators will be documented. At each study site, all efforts should be made to plan for and maintain the same blinded evaluator for all assessments throughout the study. To account for illness or unplanned absence of the blinded evaluator, it is recommended to have at least one back-up blinded evaluator trained and qualified per site. Evaluators will be re-trained on the MIHAS at regular intervals (approximately every 3 months at a minimum).

The treating investigator will also attend a MIHAS-instructional session to ensure understanding of the subject-eligibility criteria of right and left IOH volume deficit with a rating of 2 or 3 (moderate or severe) at study entry.

Additionally, three blinded IPRs will assess subject photographs using the MIHAS.

Note: For subjects randomized to treatment, the photographs assessed will be from Screening or Day 1 (Visit V1a) **and** 8 weeks post last injection (Visit V3). For subjects randomized to the control/delayed-treatment group, the photographs assessed will be from Screening, Day 1 (8 weeks from the screening visit, Visit C1a) and 8 weeks post last injection (Visit C3).

These board-certified IPRs, who are not part of the study sites, will be qualified using the methodology described for blinded evaluators above. Further details regarding photographs are provided in Section 11.2.1.2.

